Complete Title: Online Randomized Experiment Evaluating Ultra-Processed Food Warning Labels on Social Media Posts Among Teens and Young Adults

Short Title: Effects of UPF Warning Labels on Social Media Among Teens and Young Adults

Protocol Date: August 25, 2025

NCT #: NCT07227519

Study Principal Investigators:

[name]

University of Tennessee Health Science Center

Email: [contact]

[name]

Stanford University

Email: [contact]

Introduction

The goal of the analyses described here is to use data collected through an online randomized experiment to examine teens' and young adults' responses to ultra-processed food (UPF) warning labels on social media posts. These analyses assess the effect of a highly visible UPF warning label displayed beneath social media posts, compared to a control condition with no label, on consumer understanding and purchase intentions. This analysis plan pre-specifies the analyses before collecting data and therefore serves as our ex-ante planned analysis.

Study Protocol

Participants will complete an online randomized experiment. After providing informed consent, they will be randomized to one of two trial arms: (1) UPF warning labels or (2) no-label control. Participants will view four social media posts (presented in random order; all feature UPF) based on real Instagram posts from leading food and beverage companies. Labels will be shown according to participants' assigned trial arm. Participants will then respond to survey questions assessing consumer understanding, purchase intentions, perceived healthfulness, perceptions of control over healthy eating, and policy support for ultra-processed food warning labels. At the end of the UPF survey, participants will also answer an open-ended question on their understanding of the term "ultra-processed food."

Statistical Considerations

General Principles

We will use a two-sided critical alpha of 0.05 for all statistical tests. All confidence intervals will be two-sided and set at the 95% level. Analyses will be conducted on an intent-to-treat basis and will not be adjusted for any covariates, given the randomized design. Missing data will be handled in linear mixed models through maximum likelihood estimation (assumes missing at random [MAR]). Given the exploratory nature of the study, we will not adjust p-values for multiple comparisons.

Primary Outcome

The primary outcomes are consumer understanding and purchase intentions, each analyzed as repeated measures at the post level:

1. **Consumer understanding** will be measured by whether participants correctly identify the product featured in each post as UPF. Responses will be coded as correct if participants select "Yes" when asked whether they think the product featured in the post is UPF; "No" and "*I don't know*" will be coded as incorrect.
2. **Purchase intentions** will be measured for each social media post by asking participants how likely they would buy the product in the next week using a 1–5 Likert scale, with 5 indicating "*very likely*" (treated continuously).

Secondary Outcomes

The secondary outcomes are perceived healthfulness (analyzed as a repeated measure at the post level), and perceptions of control over healthy eating and policy support (both analyzed at the participant level as each participant answered these questions only once after viewing all posts):

1. **Perceived healthfulness** will be measured for each social media post by asking participants how healthy the product seems to them using a 1–5 Likert scale, with 5 indicating “*very healthy*” (treated continuously).
2. **Perceptions of control over healthy eating** will be measured by participants’ categorical responses to how an UPF warning label would make them feel. Response options will be coded as follows: “*More in control of making healthy eating decisions*” will be coded as 1, while “*Less in control of making healthy eating decisions*” and “*Neither less nor more in control of making healthy eating decisions*” will be coded as 0.
3. **Policy support for ultra-processed food warning labels** will be measured by asking participants, “Would you oppose or support a policy requiring these labels on social media advertisements for ultra-processed foods and beverages?” using a 1–5 Likert scale, with 5 indicating “*strongly support*” (treated continuously).

Statistical Methods

1. We will describe participant characteristics by trial arm. We will use means and standard deviations to characterize continuous variables and frequencies and percentages to characterize categorical variables. For the open-ended question on the participants’ understanding of the term “ultra-processed” (UPF understanding) we will develop a codebook using a hybrid inductive-deductive approach, and two independent reviewers will categorize the responses into ‘low,’ ‘moderate,’ and ‘high’ understanding.
2. Analyses of the primary outcome:
 - a. We will evaluate the effects of UPF warning labels on consumer understanding using a linear probability mixed model with random intercepts to account for repeated measures within participants. Consumer understanding (binary indicator) will be regressed on trial arm (warning label vs. no-label control). We will report the marginal predicted probability of consumer understanding in each group, as well as the average differential effect (ADE), defined as the risk difference (i.e., the difference in predicted probability between the warning label group and the control group). We opted for a linear probability mixed model rather than a logistic mixed model because we are interested in estimating risk differences.
 - b. We will evaluate the effect of UPF warning labels on purchase intentions using linear mixed models with random intercepts to account for repeated measures within participants. Purchase intention will be regressed on trial arm, and we will estimate and report the average purchase intention for each group, as well as the ADE.

c. We will test whether the effects of UPF warning labels on the co-primary outcomes (consumer understanding and purchase intentions) differ by age group (teens vs. young adults) and gender (male vs. female). To test for moderation, we will regress each primary outcome on intervention assignment and include interaction terms between intervention assignment and each moderator, using separate mixed models. We will test the significance of the interaction terms and, if significant, report the marginal effects of the UPF warning labels at each level of the moderator.

3. Analyses of secondary outcomes:

- a. We will use the same model from 2b to evaluate the effects of UPF warning labels on perceived healthfulness. Perceived healthfulness will be regressed on trial arm (warning label vs. control), and we will estimate and report the average perceived healthfulness for each group, as well as the ADE.
- b. We will describe the percentage of participants (pooled across trial arms) who report increased control over healthy eating. Similarly, we will describe the percentage of participants who report supporting requiring UPF warnings. We will additionally describe these percentages stratified by age group (teens vs. young adults) and gender (male vs. female).

4. Exploratory Analysis:

- a. We will use chi-square tests to compare the distribution of UPF understanding categories (low/moderate/high) between trial arms. If the distributions do not differ significantly, we will proceed to test participants' understanding of the term "ultra-processed food" as a moderator in section 4b. This step is to make sure that being exposed to the warning labels does not influence their understanding of the term.
- b. We will examine whether participants' understanding of the term "ultra-processed food" moderates the effect of the label on consumer understanding, purchase intention, perceived healthfulness, perceptions of control over healthy eating, and policy support for UPF warning labels. Moderation will be tested by adding UPF understanding and its interaction with trial arm to the mixed models described in sections 2 and 3. If interactions are significant, we will report stratified effects.

5. Additional considerations and sensitivity analyses:

- a. If models fail to converge for the repeated measures (unlikely), we will test simpler covariance structures.
- b. For repeated measures, we will additionally add fixed effects for social media posts in the mixed models to adjust for any systematic differences across the social media posts.

- c. For consumer understanding (binary), we will conduct sensitivity analyses using Poisson GEE models with a log link (to estimate risk ratios for consumer understanding) and robust standard errors.

Sample Size Needs

We plan to collect data from 1,000 participants. With 80% power and a two-sided alpha of 0.05, we can detect an effect size of approximately Cohen's $d = 0.18$ for non-repeated-measures outcomes. For repeated measures, assuming four repeated measures per participant, the minimal detectable d is approximately 0.13–0.16, assuming within-person correlation $\rho=0.4–0.7$. These represent small effect sizes, but ones that are meaningful at the population level.

Exclusions and Outliers

We will exclude participants who complete the survey implausibly quickly (defined as completing in less than one-third of the median completion time).

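### Does leaving age group and gender out of the main arm comparisons weaken the analysis?

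*SAP*

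**What the plan says.** Under Statistical Considerations, General Principles, the SAP states: "Analyses will be conducted on an intent-to-treat basis and will not be adjusted for any covariates, given the randomized design". The Introduction says when this was fixed: "This analysis plan pre-specifies the analyses before collecting data and therefore serves as our ex-ante planned analysis".

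The models follow that principle. In 2a, "Consumer understanding (binary indicator) will be regressed on trial arm (warning label vs. no-label control"). In 2b, "Purchase intention will be regressed on trial arm". In 3a, "Perceived healthfulness will be regressed on trial arm (warning label vs. control"). Each has a random intercept for participant and no participant characteristic.

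Age group and gender appear in two other places. Section 2c tests whether the label effects on the co-primary outcomes "differ by age group (teens vs. young adults) and gender (male vs. female"). Section 3b gives descriptive percentages "stratified by age group (teens vs. young adults) and gender (male vs. female"). Section 5b adds post fixed effects as a sensitivity analysis. Sample Size Needs gives a detectable d of about 0.18 for a single measure, and of about 0.13–0.16 for four posts with a within-person correlation of 0.4–0.7.

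**The concern.** The reason given for not adjusting covers only half of the usual argument. Randomisation removes the need to adjust for bias, but it does not show that a prognostic covariate has nothing to offer. Covariate adjustment in a randomised comparison is normally done for precision. If teens and young adults, or males and females, differ in their average response, that variation between people stays in the error of the arm contrast.

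The plan already intends to use both factors, so including them would seem to cost little. In these linear models the adjusted arm coefficient targets the same risk difference or mean difference, so interpretation would not change. At stake would be somewhat wider intervals and slightly lower power for both co-primary outcomes and for perceived healthfulness. The choice also has to be made before data collection to be credible.

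**Working it through.** **Inputs from the SAP.** N = 1,000, two-sided alpha 0.05, 80% power, four posts per participant, within-person correlation ρ = 0.4–0.7.

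**Assumptions.** Allocation is 1:1 (500 per arm; the SAP gives no ratio), with complete answers to all four posts and no exclusions. The share of variance explained by age group and gender (R²) is also assumed, because the SAP gives no figure. It refers here to the variance of a participant's mean over the four posts, and is varied over 0%, 1%, 2% and 5%.

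**Step 1: reproduce the plan's figures without covariates.**

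- Single measure: d = (1.960 + 0.842) × √(2/500) = 0.177, against a stated 0.18.
- Variance of a four-post mean, in units of the single-post variance: (1 + 3ρ)/4 = 0.55 at ρ = 0.4 and 0.775 at ρ = 0.7.
- Repeated measures: 0.177 × √0.55 = 0.131 and 0.177 × √0.775 = 0.156, against a stated 0.13–0.16.

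The power statement therefore does not rely on adjustment.

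**Step 2: what adjustment would change.** With k added covariate terms, the expected ratio of adjusted to unadjusted standard error is about

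r = √[(1 − R²) × (1 + k/(N − k − 3))].

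The second factor is the price of chance imbalance and lost degrees of freedom. For the two binary factors as the SAP defines them, k = 2 and that factor is 1 + 2/995 = 1.00201. Power at the effect that has 80% power unadjusted is Φ(2.802/r − 1.960).

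| Assumed R² | Change in SE | Power | Detectable d, ρ = 0.4 | Detectable d, ρ = 0.7 |
|---|---|---|---|---|
| unadjusted | – | 80.0% | 0.1314 | 0.1560 |
| 0% | +0.10% | 79.9% | 0.1315 | 0.1561 |
| 1% | −0.40% | 80.3% | 0.1309 | 0.1554 |
| 2% | −0.91% | 80.7% | 0.1302 | 0.1546 |
| 5% | −2.43% | 81.9% | 0.1282 | 0.1522 |

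A simulation of 4,000 trials per case, with two binary covariates, gave mean model SE changes of +0.10%, −0.41% and −2.43% at R² of 0%, 1% and 5%, in agreement with the formula. If extra categories (other, missing) raised the count to k = 4, the changes at 0%, 1%, 2% and 5% would be +0.20%, −0.30%, −0.81% and −2.34%.

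**Step 3: how large a group difference this needs.** Adjustment breaks even at R² = 1 − 995/997 = 0.20% for k = 2, or 1 − 993/997 = 0.40% for k = 4. For one evenly split factor, the gap between its two groups that gives a stated R² is 2 × √(R² × variance of the mean), in single-post SDs. At R² = 5% this is 2 × √(0.05 × 0.55) = 0.33 SD to 2 × √(0.05 × 0.775) = 0.39 SD. That is about 2.5 times the label effect the repeated-measures design is sized to detect (0.33/0.131 and 0.39/0.156). The SAP neither supports nor rules out such a gap.

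**Step 4: consistency of the text.** The General Principles sentence and models 2a, 2b and 3a agree. In 2c the factors are there to estimate interactions, and in 3b to describe subgroups; neither use commits the plan to them as covariates in the main comparison. Section 5b concerns the posts, not participant characteristics, and is labelled a sensitivity analysis. No passage contradicts another.

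**The case for a change.** The strongest case for adjustment is that the cost and the possible gain are unequal. If neither factor matters, two extra terms cost about 2 participants in 1,000 (1,000/1.00201 ≈ 998). If R² is 5%, the gain is worth about 51 (1,000/0.9757² ≈ 1,051). Break-even is low, and the estimand stays the same. Section 5b is no substitute: every participant sees all four posts, so with complete answers the post effects leave the arm estimate and its standard error essentially unchanged. If R² is defined on single-post responses instead, 5% corresponds to 9.1% of the participant-mean variance at ρ = 0.4 (0.05/0.55). The SE then falls by 4.6% and power reaches 83.5%; at ρ = 0.7 the fall is 3.2%.

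All of this stands as arithmetic, and a statistician who prespecified adjustment would be making a sound choice. It is also fair that randomisation alone is an incomplete reason for not adjusting. But the larger gains rest on prognostic strength that the document does not give.

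Adjustment would also need further decisions. The group predictions reported in 2a and 2b would need a stated covariate distribution to average over. Section 4b works by "adding UPF understanding and its interaction with trial arm to the mixed models described in sections 2 and 3", so it would inherit the covariates. Section 2c, which uses separate models for each moderator, would need aligning with the new main model, and 5c would need a stated comparator. The SAP also does not say whether age group and gender are asked before the posts are shown. The present arm-only specification raises none of these questions.

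**Conclusion.** The concern does not hold. The SAP makes an explicit, prespecified choice that gives an unbiased comparison, applies it consistently in 2a, 2b and 3a, and states detectable effects that are correct for that choice. It nowhere claims that the unadjusted analysis is the most precise one available.

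For R² of 0–5% of the participant-mean variance and two binary terms, the forgone effect runs from a 0.10% loss to a 2.43% gain in standard error, or −0.1 to +1.9 points of power. At R² of 1–2% the detectable effects still round to the SAP's own 0.13 and 0.16 or 0.15, a shift of at most about 0.001. These figures assume 1:1 allocation, complete answers and 1,000 analysed participants; at 900 the range for R² of 1–5% is a 0.39–2.42% gain, practically the same as at 1,000. Only a strong association of age group or gender with the outcomes would make the difference material, and the document gives no basis for assuming one. Whether to adjust is a trade-off on which reasonable statisticians differ, and the plan needs no correction here.

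### No robust standard errors are named for the linear probability mixed model of consumer understanding; the primary test is sound, but the interaction tests, chiefly exploratory 4b, can drift from 5%

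*SAP*

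**What the plan says.** Consumer understanding is a co-primary outcome, scored correct or incorrect for each of four posts, with a don't-know answer scored incorrect (SAP, Primary Outcome). Item 2a fits it "using a linear probability mixed model with random intercepts to account for repeated measures within participants". The reason given is the scale of the effect: "We opted for a linear probability mixed model rather than a logistic mixed model because we are interested in estimating risk differences". General Principles specifies maximum likelihood for the mixed models and says "We will use a two-sided critical alpha of 0.05 for all statistical tests".

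Item 2c adds arm-by-age-group and arm-by-gender interactions, in separate mixed models: "We will test the significance of the interaction terms and, if significant, report the marginal effects of the UPF warning labels". Exploratory item 4b does the same with low, moderate or high understanding of the term: "Moderation will be tested by adding UPF understanding and its interaction with trial arm to the mixed models described in sections 2 and 3". It runs only if the test in 4a is not significant.

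No variance estimator is named for any of these models. Robust standard errors appear once, in 5c, for "Poisson GEE models with a log link (to estimate risk ratios for consumer understanding) and robust standard errors".

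**The concern.** A random-intercept linear model has one residual variance and one intercept variance for all participants. The random intercept deals with correlation within a person. It does not deal with a variance that changes with the success rate, as p(1-p) does. Fitted by maximum likelihood with its usual standard errors, the model therefore applies an average variance to every arm and subgroup.

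Items 5a (convergence) and 5b (post fixed effects) do not address this. Item 5c does not either, because an interaction on the ratio scale tests a different null hypothesis from one on the risk-difference scale.

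What is at stake is limited. In 2c and 4b the interaction test decides whether subgroup effects are reported, so its error rate should be the stated 0.05. Item 4b is the more exposed. Its moderator, understanding the term, lies close to the outcome, recognising such a product, so base rates may well differ between groups, and nothing makes the three groups equal in size.

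**Working it through.** **Inputs from the SAP.** Two-sided alpha 0.05 (General Principles); 1,000 participants, 80% power, four posts, within-person correlation ρ of 0.4 to 0.7 (Sample Size Needs); 0/1 outcome (Primary Outcome).

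**Assumed, because the SAP does not give them.** 1:1 allocation; control rates; subgroup shares; a label effect of +10 points in every subgroup, so that no interaction exists; the same ρ in all groups; complete data; the three-level moderator tested with 2 degrees of freedom.

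**1. The SAP's own figures.** d = (1.960 + 0.842) × √(4/1000) = 0.177. Multiplying by √((1+3ρ)/4) gives 0.131 at ρ = 0.4 and 0.156 at ρ = 0.7. These match the stated 0.18 and 0.13–0.16; the sample size is not in question.

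**2. General formula.** A participant's mean over four posts has variance p(1-p)(1+3ρ)/4, so ρ cancels from ratios of standard errors. Write v = p(1-p) for each cell and s for the cell's share of participants.
- Model-based squared SE is proportional to (Σ s·v) × Σ(1/s).
- True squared SE is proportional to Σ(v/s).
- R = √(model-based / true), and actual type I error = 2(1 − Φ(1.96 R)).

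**3. Primary risk difference.** With equal arms the pooled variance is (v0+v1)/2, so the model-based and true values coincide: R = 1 and the error is 5.0% at any pair of rates. A 480/520 split with rates of 50 vs 80% gives 5.2%.

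**4. Two-level interaction, 30% minority share.** Cell shares are 0.15, 0.15, 0.35, 0.35, and Σ(1/s) = 19.048.
- Minority 50/60%, majority 80/90% (control/label): v = 0.25, 0.24, 0.16, 0.09. Pooled = 0.15×0.49 + 0.35×0.25 = 0.161. Model-based = 0.161×19.048 = 3.067. True = 0.49/0.15 + 0.25/0.35 = 3.981. R = 0.878, error 8.5%.
- Minority 40/50%, majority 50/60%: v sums to 0.49 in each subgroup, so R = 1 and the error is 5.0%.

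| Control rates, minority vs majority | Type I error | Rates swapped |
|---|---|---|
| 40 vs 50% | 5.0% | 5.0% |
| 35 vs 55% | 5.0% | 5.0% |
| 30 vs 50% | 4.6% | 5.4% |
| 50 vs 60% | 5.4% | 4.6% |
| 50 vs 70% | 6.4% | 3.8% |
| 70 vs 80% | 7.0% | 3.4% |
| 50 vs 80% | 8.5% | 2.6% |

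With equal subgroups every row is 5.0%. At a 40% share, with the smaller group having the larger p(1-p), gaps of 50 vs 60, 60 vs 70 and 70 vs 80% give 5.2, 5.5 and 5.9%.

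**5. Three-level interaction (as in 4b).** The Wald statistic is a weighted sum of two chi-squares, with weights equal to the eigenvalues of the true covariance times the inverse of the pooled covariance. It is compared with 5.99.
- Control 35/45/55%: 5.0% with shares 20/30/50 or 50/30/20.
- Control 40/60/80%: 5.1% with equal thirds; 7.6% with shares 20/30/50 (weights 1.329 and 0.995); 3.6% with shares 50/30/20 (weights 1.082 and 0.685).

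**6. Per-arm confidence intervals, if given with the 2a probabilities.** R = √(mean of the two v / own v), and coverage = 2Φ(1.96 R) − 1.
- 50 vs 80%: mean v = 0.205, R = 0.906 and 1.132, coverage 92.4% (control) and 97.3% (label).
- 50 vs 58%: d = 0.08/√0.2468 = 0.16, the upper end of the SAP's repeated-measures range. Coverage is 94.9% and 95.1%.

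**7. Simulation check.** Beta-binomial responses, 1,000 people, four posts, 10,000 runs each at ρ = 0.4 and 0.7.

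| Scenario | Model-based | Clustered robust |
|---|---|---|
| Two-level, 30% share, 50 vs 80% | 7.9–8.6% | 4.6–4.8% |
| Same, rates swapped | 2.3–2.5% | 4.6–4.9% |
| Three-level 40/60/80%, shares 20/30/50 | 7.7% | 5.1–5.2% |
| Same rates, shares 50/30/20 | 3.7–3.8% | 5.1–5.3% |

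A separate simulation at ρ = 0.5 gave 4.6–5.5% with robust variances in every scenario.

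**The case against.** The strongest reply has three parts.

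First, this is a silence and not an error: the SAP never says that model-based standard errors will be used. That is true. But the usual output of a maximum-likelihood mixed model is the pooled-variance standard error, and the SAP names robust ones where it plans them (5c). Naming them here too would settle the matter before data are seen.

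Second, the larger distortions need high control rates or wide gaps. This stands. At mid-range rates a 10- or 20-point gap with unequal groups leaves the error at 5.0%, and because don't-know answers count as incorrect, control rates below 50% are quite possible.

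Third, the study calls itself exploratory and does not adjust for multiplicity. Item 2c alone has four interaction tests (two outcomes, two moderators); if independent, the chance of at least one false positive is 1 − 0.95⁴ = 18.5%. A shift of a point or two in one test is small beside that. This limits the priority. It does not make a test that misses its nominal level preferable to one that keeps it at almost no cost.

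A reader might also infer that a linear model for a 0/1 outcome invalidates the primary analysis. The SAP does not support that: the risk difference is the declared target, and the test of it holds 5% at about 1:1.

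**Conclusion.** The point holds as a small one. The primary risk difference is unaffected at about 1:1 allocation (the ratio is not stated), and 2c is essentially unaffected if the age and gender groups are of similar size. The interaction tests depart from 5% only when subgroups differ in both size and p(1-p). Under the assumed scenarios at a 30% minority share, the two-level error runs from no distortion at mid-range rates to 2.6% or 8.5% at 50 vs 80%. For a three-level moderator it is 5.0% at 35/45/55%, and 3.6% or 7.6% at 40/60/80% with unequal shares.

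It would be tempting to say that the interaction tests are inflated. The documents do not support this: they give no rates or shares, and the error is conservative when the larger subgroup has the larger p(1-p). Per-arm intervals are implied rather than promised, and are noticeably off only if the label effect is large. No coverage figure is claimed for subgroup label effects, because these are reported only after a significant interaction.

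**What to change.** Add to Statistical Methods, for 2a, 2c and 4b: for consumer understanding, all standard errors, confidence intervals and tests from the linear probability mixed model, including marginal probabilities, the risk difference, interactions and any subgroup effects, will use participant-clustered robust (sandwich) standard errors.

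The cost is one sentence. Model, estimand, point estimates, sample size and the maximum-likelihood handling of missing posts stay as they are. The downside is slightly more variable standard errors, which is minor with 1,000 participants. The change corrects the variance only; it does not remove the selection that comes from reporting subgroup effects only after a significant interaction. Low priority.

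### Label effects by age group and gender are promised only if the interaction is significant, and no interaction estimate or interval is promised otherwise

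*SAP*

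**What the plan says.** Statistical Methods 2c names two moderators, age group (teens or young adults) and gender (male or female), for the co-primary outcomes of consumer understanding and purchase intentions. That makes four interaction tests. The reporting commitment that follows the test is: "if significant, report the marginal effects of the UPF warning labels at each level of the moderator". Item 4b, which concerns participants' understanding of the term UPF, ends in the same way: "If interactions are significant, we will report stratified effects".

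General Principles sets the threshold ("We will use a two-sided critical alpha of 0.05 for all statistical tests") and declines any correction ("Given the exploratory nature of the study, we will not adjust p-values for multiple comparisons").

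Other results carry no such condition. Items 2a, 2b and 3a report the arm means or probabilities and the overall label effect outright. Item 3b gives percentages by age group and gender outright, but these are pooled across arms and so are not label effects. Sample Size Needs gives detectable effects for the overall arm comparison only and none for an interaction.

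**The concern.** Requiring a significant interaction before *interpreting* a subgroup difference is good practice. Making the *reporting of estimates* depend on that test is a different rule, because what gets displayed then depends on the result.

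Two consequences follow if the interaction test has modest power:

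- A non-significant test would be reported with no committed interval, so the reader could not see how large a difference between teens and young adults remains compatible with the data. Absence of a significant interaction is easily taken for equality of effect.
- The contrasts that are displayed are those whose estimated interaction came out large, and such estimates overstate the true interaction on average.

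The stakes are limited to the moderation results. However, both age groups are in the trial's title, and 2c sits under the primary-outcome analyses, so readers will look for these effects.

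**Working it through.** **Inputs from the SAP.** Total sample: "We plan to collect data from 1,000 participants". Arms: "they will be randomized to one of two trial arms". Design basis: "With 80% power and a two-sided alpha of 0.05". Four posts per participant and within-person correlation ρ from 0.4 to 0.7 (Sample Size Needs).

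**Assumptions not in the SAP.** Allocation 1:1 (500 per arm); subgroup share s of 0.5, with 0.3 and 0.2 also shown; equal variances; no loss to the speed exclusion. Everything is on the standardised continuous scale, so it is approximate for the linear probability model.

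**Step 1: reproduce the plan's figures.** The multiplier is 1.960 + 0.842 = 2.802.

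- Single measure: 2.802 × √(2/500) = 0.177, against the stated 0.18.
- Repeated measures: SE = √(2/500) × √((1+3ρ)/4), which is 0.0469 at ρ = 0.4 and 0.0557 at ρ = 0.7. Multiplying by 2.802 gives 0.131 and 0.156. The SAP says "the minimal detectable d is approximately 0.13–0.16", so it reproduces, with 0.13 belonging to ρ = 0.4 and 0.16 to ρ = 0.7.

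**Step 2: interaction with a two-level, between-person moderator.** The interaction is the difference of two subgroup effects, with variances SE²/s and SE²/(1−s). Hence SE(interaction) = SE / √(s(1−s)), which is 2 × SE at s = 0.5: 0.0938 (ρ = 0.4) and 0.1114 (ρ = 0.7).

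- Detectable interaction at 80% power: 2.802 × 0.0938 = 0.263 and 2.802 × 0.1114 = 0.312.
- 95% CI half-width: 1.96 × 0.0938 = 0.18 and 1.96 × 0.1114 = 0.22. This is wider than the whole detectable main effect.

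**Step 3: power for an interaction equal to the detectable main effect.** Here δ = true interaction / SE(interaction) = 2.802 × √(s(1−s)), which does not depend on ρ when each effect is paired with its own ρ. Power = Φ(δ − 1.96) + Φ(−δ − 1.96). At s = 0.5, δ = 1.401 and power = Φ(−0.559) + Φ(−3.361) = 0.288. Using the rounded effects gives 28% (0.13 at ρ = 0.4) to 30% (0.16 at ρ = 0.7).

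**Step 4: inflation given significance.** This is the mean absolute significant estimate divided by the true interaction:
[δΦ(δ−1.96) + φ(δ−1.96) − δΦ(−δ−1.96) + φ(δ+1.96)] / (power × δ). At s = 0.5: (0.4034 + 0.3412 − 0.0005 + 0.0014) / (0.2884 × 1.401) ≈ 1.85. Simulation from the same normal distribution gives 1.84.

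| Subgroup split | Detectable interaction (ρ 0.4 to 0.7) | Power, interaction = detectable main effect | Inflation if significant |
|---|---|---|---|
| 50:50 | 0.26–0.31 | 29% | about 1.85 |
| 30:70 | 0.29–0.34 | 25% | about 2.0 |
| 20:80 | 0.33–0.39 | 20% | about 2.25 |

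At 50:50, subgroup effects would then go unreported with probability 1 − 0.288 = 0.71.

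**Step 5: dependence on the size of the interaction (50:50).** At half the detectable main effect, power is about 11% and inflation about 3.5. At 0.26–0.31 SD, power is 80% and inflation about 1.1.

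**Step 6: what selection does to each subgroup effect.** At 50:50, selecting on the interaction moves the two subgroup estimates in opposite directions, each by half the interaction's bias: 0.85 × 0.131 / 2 = 0.056 SD at ρ = 0.4, and 0.85 × 0.156 / 2 = 0.066 SD at ρ = 0.7.

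**The case against.** The plan fixes moderators, outcomes, models and follow-up rule before data collection, calls the study exploratory, and requires an interaction test before showing subgroups. That is a recognised guard against over-reading subgroup tables, and with four unadjusted tests the guard has value. This stands, and it is why the test should stay. It supports conditioning the interpretation; it does not require conditioning the display.

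A reader might infer more than the SAP supports in three ways:

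- *Moderation results will be hidden or selectively published.* The SAP does not say that interaction tests, estimates or p-values will be withheld. It is silent on estimates and intervals, the rule is disclosed in advance, and overall effects are always reported. The gap is a missing commitment.
- *Every subgroup effect shown will be exaggerated.* The inflation belongs to the interaction coefficient. The two subgroup effects are pushed apart, so one moves up and the other down.
- *Interaction power is low, without qualification.* It depends on the true interaction and the subgroup shares, neither of which the SAP gives. For large interactions in balanced subgroups it is adequate.

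It is also fair to say that the calculation does not cover 4b. That moderator has three levels, two of its outcomes are measured once per participant, and it runs only if the test in 4a is non-significant. The point carries over to 4b through its wording alone.

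**Conclusion.** The concern holds as a reporting defect. Items 2c and 4b tie label effects by moderator level to a significant interaction, and nothing commits the authors to an interaction estimate or interval when the test fails. On the SAP's own sample size and correlations, a non-significant age or gender interaction would exclude little: the interval extends about 0.18–0.22 SD either side of the estimate, and an interaction as large as the detectable main effect would be missed about 70% of the time. These figures rest on 1:1 allocation and evenly split subgroups; less even splits make them worse. The overall label comparison, alpha and sample size are unaffected. This is an inexpensive improvement worth making, and not a threat to the main result.

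**What to change.** In 2c, remove the significance condition on reporting. Suggested content:

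- For each moderator and co-primary outcome, report the interaction estimate with its 95% CI and p-value, and the label effect with its 95% CI at each level of age group and gender, whatever the p-value.
- Base any conclusion about subgroup differences on the interaction estimate, and state that a non-significant interaction is not evidence of equal effects.
- In Sample Size Needs, state the detectable interaction: about 0.26–0.31 SD if subgroups are evenly split, recalculated for the shares actually expected.

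In 4b, apply the same reporting if that analysis is run.

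The cost is one table and a few sentences, with no change to the models, alpha or sample size. The small downside is that readers may over-read the subgroup estimates; printing the interaction CI beside them limits this. The change removes the selective display. It does not raise the power, nor does it shrink an interaction estimate that happens to reach significance. At 50:50, 80% power for an interaction equal to the detectable main effect would take about four times the sample (SE doubled, so 2² × 1,000 = 4,000), which is not being asked for.
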